***Naltrexone and alcohol drinking:***

Naltrexone's efficacy in reducing alcohol drinking is believed to be mediated through interactions between the endogenous opioid system and dopamine systems, specifically through antagonism of the mu-opioid receptors. The most commonly used dose of naltrexone of 50 mg/day has been shown to result in complete occupancy of the brain mu-opioid receptors (Weerts et al., 2008). Clinical trials indicate that treatment seeking drinkers who receive naltrexone at a dose of 50 mg/day in combination with a behavioral intervention have lower levels of relapse to drinking during the treatment period. However, it is important to note that not all the clinical trials conducted with naltrexone over the past decade have observed significant improvements in drinking treatment outcomes (e.g. Krystal et al., 2001), and two recent meta-analytical reports suggest that naltrexone has small to modest efficacy in preventing relapse to drinking (Bouza et al., 2004; Srisurapanont and Jarusuraisin, 2002). Moreover, while naltrexone is relatively well tolerated, the potential risk of hepatotoxicity at high doses requires caution in use in those with liver disease. A more recent multi-site trial which used a higher dose of naltrexone (100 mg/day) with medical management to enhance compliance found significant reductions of alcohol drinking with naltrexone, although again with a small effect size in the overall sample (Anton et al., 2006).

Many investigations have attempted to understand the modest efficacy of naltrexone by evaluating its mechanism of action as well as understanding factors that predict treatment response to naltrexone. Naltrexone is believed to produce its effects by blocking the GABAergic neurons that tonically inhibit the dopamine neurons that project to the nucleus accumbens from the ventral tegmental area (see Johnson, 2008). From a behavioral perspective, early studies conducted in social drinkers observed that administration of a single dose of naltrexone (50 mg) followed by an alcoholic drink resulted in more sedation and less stimulating effects of alcohol (Swift et al., 1994), and that reduction in alcohol-induced stimulation was only observed in those who had a high risk of developing alcoholism (King et al., 1997). More recent examinations of naltrexone in alcohol-dependent drinkers using self-administration paradigms (Davidson et al., 1999; O'Malley et al., 2002; Drobis et al., 2003) and clinical trials (e.g. Richardson et al., 2008) suggest that the efficacy of naltrexone may be related to its ability to reduce craving or urge to drink. Myrick et al. (2008) observed that naltrexone reduced alcohol-cue-induced activation of the ventral striatum. Similarly, naltrexone reduced alcohol-induced stimulation, positive mood, and craving experienced in response to an intravenous dose of alcohol in alcohol-dependent drinkers (Ray and Hutchinson, 2007). However, our evidence from HIC # 9912011476 suggests that naltrexone-induced reduction in drinking in FHP drinkers is not accompanied by any consistent changes in alcohol craving or stimulation.

Evaluations of predictors of treatment response to naltrexone have identified many factors including the presence of a family history of alcoholism and variants of the mu-opioid receptor gene (OPRM1 gene). Our work in HIC # 9912011476 found that alcoholics with a family history of alcoholism appear to respond better, with greater reductions in alcohol consumption than those who have a negative family history of alcoholism (Krishnan-Sarin et al., 2007). Moreover, individuals who have a variant of the OPRM1 gene (or the gene for the mu-opioid

receptor where naltrexone produces its effects) have better response to naltrexone treatment in most (Oslin et al., 2003; Oroszi et al., 2009; Anton et al., 2008) but not all (Gelernter et al., 2007) clinical trials.

In summary, the opioidergic system is an important modulator of alcohol effects and the opioid antagonist naltrexone has been shown to be effective at reducing alcohol drinking. Existing evidence also suggests that naltrexone may reduce alcohol drinking by attenuating craving for alcohol and that variants of the OPRM1 gene and family history of alcoholism may predict treatment response. However, the overall efficacy of naltrexone in reducing alcohol drinking is rather modest, with most clinical trials documenting a medium effect size. Interestingly, in our earlier project (HIC # 9912011476 ), while we observed significant naltrexone-induced reductions in drinking in FHP drinkers, these changes were not accompanied by consistent changes in alcohol craving or alcohol reward. All the above evidence suggests that there is room for improvement and a great need for medication approaches that have greater efficacy in reducing alcohol use.

#### ***Glutamate and alcohol addiction:***

The amino acid L-glutamate is the major excitatory amino acid neurotransmitter in the central nervous system. The glutamate system is involved in fast synaptic transmission as well as plasticity and higher cognitive functions. Glutamate produces its effects by binding to one of three different types of ionotropic postsynaptic receptors: the *N*-methyl-D-aspartate (NMDA) receptor, the alpha-amino-3-hydroxy-5-methylisoxazole-4-propionate (AMPA), and the kainate receptor (Parsons et al., 2005). Glutamate also produces some of its effects by binding to metabotropic glutamate receptors (mGluR's) located in the perisynaptic and presynaptic regions (Gass and Olive, 2008). Most important, glutamate is one of the primary neurochemical substrates of synaptic plasticity, and it is believed that neuroadaptations in glutamatergic transmission produced by chronic drug use leads to compulsive drug use (Gass and Olive, 2008; Koob et al., 2009; Kalivas et al., 2005).

Alcohol appears to have paradoxical effects on this system, with increases in extracellular levels of glutamate observed in a variety of brain regions, both after administration of low doses of alcohol as well as following withdrawal from chronic alcohol use. The NMDA receptor is one of the primary high-affinity targets for ethanol in the brain (Grant and Lovinger, 1995), and acute ethanol administration dose-dependently attenuates NMDA receptor function (Grant and Lovinger, 1995; Hoffman et al., 1990; Lovinger et al., 1989). Ethanol-induced modulation of NMDA receptor function is observed at doses of ethanol that produce intoxicating behavioral effects in animals (Woodward, 1999). NMDA receptors in many brain regions, including the cerebral cortex, septum, amygdala, hippocampus, locus coeruleus, cerebellum, and the VTA and nucleus accumbens, are sensitive to this effect of ethanol (see Gass and Olive, 2008). Preclinical studies indicate that chronic exposure to ethanol inhalation enhances glutamatergic synaptic transmission in the nucleus (Nie et al., 1993), suggesting that NMDA receptors are up-regulated by chronic ethanol exposure. During ethanol withdrawal, this glutamatergic up-regulation and subsequent enhanced Ca2+ influx contribute to ethanol withdrawal and associated neurotoxicity (Hoffman et al., 1990; Tsai et al., 1995; Tsai and Coyle, 1998). NMDA receptors also appear to be essential for developing tolerance to many of ethanol's behavioral effects (Rafi-Tari et al., 1996; Szabo et al., 1994; Wu et al., 1993). Ethanol also appears to inhibit the function of AMPA and KA receptors, but these receptors seem to be less sensitive to inhibition by ethanol, which is only observed at higher concentrations.

Preclinical drug discrimination studies indicate that NMDA antagonists have ethanol-like discriminative stimulus properties, particularly at higher training doses of ethanol (Grant and Columbo, 1993; Hundt et al., 1998). There have been some examinations of sub-anesthetic doses of NMDA antagonists in humans (Krupitsky et al., 2001; Krystal et al., 1998; Petrakis et al., 2004; Schultz and Soyka, 2000). Anecdotal reports from healthy human subjects indicate that NMDA antagonists like PCP (Luby et al., 1959) and ketamine (Krystal et al., 1994) produce ethanol-like subjective effects. Studies conducted in alcohol-dependent subjects reported that ketamine's euphoric effects were associated with sedation and cognitive impairment. Similar to the preclinical studies, lower doses of ketamine were judged to be more alcohol-like and similar to 1-2 standard drinks, while higher doses of ketamine were judged to be similar to 8-9 alcoholic drinks (Krystal et al., 1998; Krupitsky et al., 2001; Petrakis et al., 2004).

The above evidence suggests that the NMDA-related actions of ethanol may contribute to its behavioral effects. Therefore, drugs modulating this component of ethanol's effects should attenuate ethanol intoxication and reward. In support of this, extensive preclinical and molecular evidence suggests that NMDA receptor antagonists reduce operant responding for alcohol and alcohol self-administration (Bienkowski et al., 1999; Holter et al., 1996; Holter et al., 2000; Lin and Hubbard, 1995), deprivation-induced alcohol drinking (Vengeliene et al., 2005), cue-induced reinstatement of alcohol drinking (Backstrom and Hyttia, 2004; Bachteler et al., 2005), acquisition of conditioned place preference for alcohol (Biala and Kotlinska, 1999; Boyce-Rustay and Cunningham, 2004), and sensitization to the locomotor-stimulating effects of alcohol (Broadbent and Weitemier, 1999; Meyer and Phillips, 2003; Kotlinska et al., 2007). Acamprosate, or calcium acetyl homotaurinate, an NMDA receptor modulator (Harris, 2002; Pope and Lovinger, 2000), is FDA approved for the treatment of alcohol drinking, and has been shown in preclinical and clinical studies to reduce alcohol consumption (Chick, 2003; Heyse et al., 1998; Stromberg et al., 2001; Spanagel et al., 1996; Heyser et al., 1998; Vengeliene et al., 2007). However, more recent clinical evidence questions the efficacy of this agent in reducing alcohol drinking (Anton et al., 2006). Topiramate, another agent that targets the kainate and AMPA glutamatergic system as well as extrasynaptic GABA-A receptors (see review by Krystal et al., 2006), has also shown preliminary efficacy in reducing alcohol drinking in clinical RCT (Johnson et al., 2007; see review by Kenna and colleagues, 2009); however, the agent's adverse event profile may limit its utility.

In regard to alcohol effects, preclinical evidence suggests that memantine attenuates alcohol-withdrawal-induced neurotoxicity in hippocampal neurons (Stepanyan et al., 2008), potentiates the ataxic effect of alcohol (Chen and Holmes, 2009), and reduces alcohol drinking in a schedule-induced polydipsia paradigm (Escher and Mittleman, 2006). Bisaga and Evans (2004) observed that memantine (in doses of 15 and 30 mg) was well tolerated and reduced alcohol craving in moderate social drinkers and resulted only in mild dissociative effects when combined with alcohol. Memantine, in doses of 20 mg/day and 40 mg/day, produced dose-dependent decrease in cue-induced alcohol craving in recently abstinent, alcohol-dependent participants (Krupitsky et al., 2007). Two open-label trials with memantine, at a dose of 20 mg/day, reported improvement in alcohol-related dementia (Cheon et al., 2008) and reduction in alcohol drinking and urges to drink (Arias et al., 2007). More recent evidence from a small 16 week, double-blind, placebo-controlled trial of a 40 mg/day dose in alcohol-dependent drinkers did not demonstrate any significant benefits for memantine (Evans et al., 2007); while the results of this trial raise questions about the efficacy of memantine as a stand-alone agent, it is also important to note that this trial did not examine differences in efficacy by family history of alcoholism.

Pilot evidence from our ongoing project suggests that memantine's effects are related to dose as well as family history of alcoholism; specifically, we observed that in FHP drinkers, memantine reduced alcohol-induced stimulation and alcohol craving at both the 20 mg/day and 40 mg/day doses with emerging evidence for modest reductions in drinking at the 40 mg/day dose. In contrast, memantine did not have any effects on alcohol stimulation, craving, or drinking behaviors in FHN drinkers at either of the doses examined.

#### ***N-acetyl cysteine:***

N-acetylcysteine (NAC) is an N-acetyl pro-drug of the naturally occurring amino acid cysteine. This agent is FDA-approved for use as a mucolytic agent for bronchopulmonary disorders (e.g. Grandjean et al., 2000) and as an oral or intravenous antidote to treat acetaminophen poisoning (Smilkstein et al., 1988). NAC is a precursor of glutathione synthesis and is available worldwide in intravenous, oral and nebulizer forms and is also sold over the counter in health food stores. NAC has been found to stimulate cysteine-glutamate exchange, thereby increasing non-synaptic glial release of glutamate (e.g. Baker et al., 2003) which then stimulates inhibitory presynaptic metabotropic glutamate autoreceptors to decrease vesicular release of glutamate. This mechanism is believed to mediate the reduced reinstatement of drug seeking behavior observed in animal models with the use of this agent (Baker et al., 2003; Madayag et al., 2007; Moran et al., 2005). Kalivas and colleagues (2008) have postulated that since drug self-administration down regulates the cysteine-glutamate exchanges (Kau et al., 2008) the upregulation of the exchanger via NAC administration may directly normalize drug-induced changes. While there have been no tests of the influence of NAC on alcohol behaviors there is extensive evidence with other substances. For example, NAC reduces cocaine use in cocaine dependent rodents (e.g. Madayag et al., 2007; Moran et al., 2005). Preliminary clinical trials suggest that NAC is well tolerated with minimal side effects and that it decreases cocaine craving and use in cocaine dependent humans (Larowe et al., 2006; Mardikian et al. 2007). More recent evidence suggests that NAC restores the ability to induce long-term-potentiation and long-term-depression in cocaine treated rats, possibly by indirectly stimulating mGluR2/3 and mGluR5 receptors

(Moussawi et al., 2009). Similarly encouraging results have been observed in preclinical work with opioid dependence (Zhou and Kalivas, 2008) and clinical studies involving obsessive compulsive disorder (Lafleur et al., 2006), pathological gambling (Grant et al., 2007) and nicotine dependence (Knackstedt et al., 2008).

A significant advantage of this agent is the fact that it has been safely used for several decades in adults and children (Mucomyst Package insert) and in studies evaluating long-term treatments with this agent for chronic bronchitis have found that it was cost-effective to use and generally well tolerated with mild, most commonly gastrointestinal adverse effects (Grandjean et al., 2000). Memantine, on the other hand, is associated more side effects; the tolerability of NAC relative to memantine is a strength.

In the proposed study, we will test the influence of NAC on alcohol drinking and alcohol-induced behaviors including stimulation, sedation and craving using the same ADP as our ongoing memantine study. We propose to use a dose of 2400 mg/day of NAC which was observed to be safe and tolerable in cocaine dependent participants (e.g. Larowe et al., 2006).

### ***Why combine memantine/NAC and naltrexone?***

Habitual alcohol use in alcohol-dependent heavy drinkers may be dependent not just on continued alcohol reward but also on conditioned incentive processes, like cue-induced craving and automated motivational tendencies, which are mediated by complex interactions between different neurochemical processes (Johnson et al., 2008; Krishnan-Sarin et al., 2009; Koob and Le Moal, 2008). Therefore, alcohol drinking in habitual, alcohol-dependent drinkers could be optimally reduced by combined treatment with agents that influence different behavioral and neurochemical effects of alcohol. Modulation of ventral striatal dopaminergic function by various neurotransmitters including glutamate, GABA, and opioids plays a crucial role at every stage of the addiction process, including initiation, maintenance, and relapse (Vengeliene et al., 2008). While it is very difficult to pinpoint which system contributes most to transition from initiation to compulsive alcohol use, it is widely believed that agents which target these systems may work synergistically to reduce ventral striatal activity and thus reduce reward and associated processes.

There is considerable evidence of direct and indirect interactions between the glutamate and opioid systems in mediating reward. The glutamatergic system has been shown to play a very important role in addiction to opioids like methadone (see review by Guo et al., 2009). The mu-opioid receptor system is an important modulator of glutamatergic function in rat central amygdala neurons (Zhu and Pan, 2005), and NMDA and mu-opiate receptors are co-localized in the nucleus accumbens (Gracy et al., 1997) and nucleus tractus solitarius (Huang et al., 2000). Mu-receptor antagonists have been shown to reduce glutamatergic response to acute alcohol administration in the nucleus accumbens (Nie et al., 1993). More recent evidence also suggests that chronic alcohol use may lead to increased recruitment of functional mu- and delta-opioid receptors on glutamate neurons of the central nucleus of the amygdala that may be involved in maintaining conditioned place preference for alcohol (Zhu et al., 2009).

The above evidence suggests that two agents that might work synergistically to reduce alcohol drinking behaviors are glutamatergic agents like memantine/NAC and naltrexone. This hypothesis is directly supported by the work of Kuzmin and colleagues (2008), who examined the effects of naltrexone in combination with memantine on operant alcohol self-administration in rats. The results of this investigation suggest that memantine at a dose of 1 mg/kg significantly enhanced the effect of a low dose of naltrexone (0.1 mg/kg) in inhibiting alcohol self-administration. This

evidence suggests that memantine, when combined with low-dose naltrexone, may block alcohol reinforcement and that this combination may have therapeutic value in the treatment of alcohol drinking.

We propose that combining naltrexone with memantine/NAC will target distinctive mechanisms underlying alcohol-drinking behavior. The combination will optimally suppress ventral striatal dopaminergic activity, improve striatal functioning, and restore control over alcohol-drinking behavior, and lead to optimal reduction in alcohol-drinking behaviors.

3. **Research Plan:** Provide an orderly scientific description of the study design and research procedures as they directly affect the subjects.

This project will use a within-subjects, crossover design to examine the effects of naltrexone with or without memantine or NAC on drinking and other alcohol-related behavioral measures in alcohol-dependent or abusive heavy drinkers with a positive family history of alcoholism (FHP). Non-treatment-seeking heavy drinkers will participate in three ADP lab sessions, occurring prior to medication and after the first and second weeks of medication treatment. They will also participate in two follow-up appointments at one week and one month after participation. The baseline ADP will be used to familiarize subjects with the laboratory procedures and reduce order effects in the subsequent ADP sessions. Each ADP will involve consumption of a priming alcoholic drink (0.03 mg%) at 3 pm followed by three one-hour choice drinking periods. During each hour subjects will choose between 4 alcoholic drinks (0.015 mg% each) or equivalent monetary rewards (\$3 per drink). During each 6-8-day medication outpatient treatment period (up to 13 days), subjects will receive naltrexone and be randomized to receive either 20 mg of memantine, 2400 mg of NAC or placebo, and medication doses will be tapered up and adverse events recorded on a daily basis.

The study will consist of five phases: 1) **Phase 1 (Screening):** We obtain informed consent and evaluate eligibility for the study using clinical assessments and physical exams, if eligible, participants will be scheduled for the rest of the study, 2) **Phase 2 (Baseline):** Participants will complete some memory and mood tasks, participate in the PIT task, and complete a baseline alcohol drinking paradigm (ADP), 3) **Phase 3 (Med 1):** The first 6-8day outpatient medication phase during which participants will come into our clinic every day to take the medication combination they have been assigned and participate in the second ADP on the last day of medication, (participants may be asked to take the medication for up to 13 days, based on scheduling for their overnight stay) Also, in the event that a medication appointment will be missed because the participant is unable to come to the clinic the following day, he/she will be given an extra dose of medication to take home for the next day. The participant will be called the next day as a reminder to take the medication and will also be asked about any adverse events. 5) **Phase 4 (Washout):** At least 6-8 day washout phase (length of washout based on hospital scheduling) and 6) **Phase 5 (Med 2):** Participants will be randomized to receive another medication combination for 6-8 days which will culminate in the third ADP (again, this is based on scheduling for the overnight at the hospital and can be extended to 13 days). In the event that a participant is unable to make it to one of the overnight visits, and needs to discontinue one of the medication periods early due to personal circumstances, we would like to have the option of restarting the medication. We do not believe that this will increase risk to participants since they would have already taken the medications during an earlier phase. It is essential that participants complete all parts of the study for us to be able to use the data to evaluate the effects of combining naltrexone and memantine on drinking behaviors.

Once all phases are complete, participants will be scheduled for a 1-week follow up appointment. We will record any remaining adverse events and assess drinking behavior. A clinical psychologist will talk to all participants about their drinking behavior and if they are interested will provide them with treatment referrals. The one-week and one-month follow-up sessions will be conducted with all participants, even those who drop out during the course of the study.

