**Table 1**

PERIOD	TIMING	PROCEDURES
ADP	10 am	Breath alcohol levels, AUQ, YCS, TLFB, SAFTEE, CADSS, Vitals Administer last doses of medications
	11 am	Approach Avoidance Task, Impulsivity tasks; Self report and Laboratory measures
	12 pm	Lunch and Smoke Break for smokers
	1 pm	Insertion of IV for blood alcohol draws
	2 pm	Start of baseline; AUQ, YCS, BAES, Vitals; Smoke break for smokers
	2:30 pm	AUQ, YCS, BAES, Vitals
	2:45pm	YCS
	2:50 pm	Alcohol cue exposure to preparation of priming drink (PD)
	2:59 pm	YCS
	3 pm	Priming dose period: Instruct participant to consume PD (0.03g/dl) in five minutes

	3:10 pm	Blood alcohol, AUQ, YCS, BAES
	3:20 pm	Blood alcohol, AUQ, YCS, Vitals
	3:30 pm	Blood alcohol, AUQ, YCS, BAES
	3:40 pm	Blood alcohol, AUQ, Vitals
	3:50 pm	Blood alcohol, AUQ, YCS, BAES
	4 pm First tray	1 st Self-administration (SA) period: Bring in first tray of 4 drinks (each designed to raise BAL by .015 g/dl) and drinking tab (\$12); Instruct participants on choice of drinks versus money.
	4:30 pm	AUQ, YCS, BAES
	5 pm Second tray	Blood alcohol, AUQ, BAES, Vitals @ 4:55 pm 2 nd SA period: Remove first tray and bring in second tray: Present participant with 4 drinks (each will raise BAL by .015 g/dl) and drinking tab (\$12); repeat instructions
	5:30 pm	AUQ, YCS, BAES
	6 pm Third tray	Blood alcohol, AUQ, BAES, Vitals @ 5:55 pm 2 nd SA period: Remove second tray and bring in third tray: Present participant with 4 drinks (each will raise BAL by .015 g/dl) and drinking tab (\$12); repeat instructions
	6:30 pm	AUQ, YCS, BAES
	7 pm	Blood alcohol, AUQ, BAES, YCS, Vitals
	7:30 pm	Dinner
	8 pm	Breath Alcohol, AUQ, YCS, BAES, Vitals
	9 pm	Breath Alcohol, AUQ, YCS, BAES, Vitals
	10 pm	Breath alcohol, AUQ, YCS, BAES, Vitals
Discharge	7 am	Breath alcohol, AUQ, YCS, Vitals, CADSS, BPRS

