i) Psychophysiological Measures: These will include heart rate and blood pressure monitored using a Critikon Dinamap while skin temperature will be measured using Yellow Springs Instruments 4600 precision thermometer. The cuff of the Dinamap will be on the subject's dominant arm while the probe of will be attached to the middle finger of the subject's non-dominant arm. These data will be further used to examine the safety of using the medication combination during alcohol self-administration.

4. **Statistical Considerations:** Describe the statistical analyses that support the study design.

All outcomes will be summarized descriptively and assessed for normality prior to analysis using normal probability plots and Kolmogorov test statistics. Transformations or nonparametric analyses will be performed as necessary. In the mixed models described below, the correlation between repeated measures on an individual will be modeled using random effects and/or structured variance-covariance matrices. The best-fitting variance-covariance structure will be determined by information criterion. The mixed-effects approach is advantageous in that it is unaffected by randomly missing data and allows greater flexibility in modeling the correlation structure of repeated-measures data (Gueorguieva and Krystal, 2004). In the models below, we will test for order effects, although any such effects should be greatly minimized with the inclusion of the baseline session. All tests will be two-sided and considered statistically significant at alpha=.05. Significance levels for secondary comparisons will be adjusted for multiple tests using the Bonferroni correction, basing the adjustment on the number of conceptually related statistical tests within each hypothesis.

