Memantine has been used in the treatment of patients with Parkinson's disease [48], dementia [49-51] and neurogenic bladder dysfunction in spasticity [52]. The drug was also found to be stimulating or vigilance-enhancing in comatose patients [53]. Memantine induces open-channel blockade of NMDA receptors and has been observed to be partially trapped in NMDA receptor channels. There have been a number of studies of memantine in healthy volunteers. Memantine has been shown to increase intracortical inhibition and reduce intracortical facilitation [54] and found to have no significant effects on mood, attention or immediate and delayed verbal and visuospatial memory [55]. Memantine has vigilance-enhancing effects in healthy elderly volunteers [56] but no effects on a series of perceptual and psychomotor tasks, including temporal discrimination, reaction time, critical flicker fusion frequency and signal detection [57]. Memantine is completely absorbed from the GI tract and maximum plasma concentrations occur between 3-8 hours after oral administration. It is 100% bioavailable after oral administration and has been shown to have a linear pharmacokinetic profile that is not influenced by age, sex or food (Forest Labs, data on file). Approximately 80% of the agent circulates as unchanged parent drug, the mean terminal elimination half-life is 60-100 hours and it is eliminated renally [43]. Memantine was well tolerated in randomized double-blind, placebo-controlled trials for patients with moderately severe to severe dementia, moderate to severe Alzheimer's disease as well as vascular dementia [43, 58, 59]. The most common adverse events observed in clinical trials are diarrhea, insomnia, dizziness, headache, constipation, and confusion [60]. In patients with severe renal impairment or hepatic problems the use of memantine has not been systematically evaluated and is not recommended.

Naltrexone, an opioid antagonist, is widely used in the treatment of opioid addiction and more recently has been found to be beneficial in the treatment of alcoholism. Numerous studies have found naltrexone use to be safe and rarely associated with toxicity or severe side effects. The most frequent reported side effects are gastrointestinal in nature. Those include epigastric pain,

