Because this study may not have direct benefits to the individual participant, subjects will be offered payment for their participation. Subjects will have the opportunity to receive up to \$2103 for completing all phases of the study. Payment for the screening interview will be \$50, and they will receive an additional \$50 for the physical examination; we have found that payments for these appointments encourages attendance as scheduled. Subjects will also receive \$50 for the PIT task, \$150 for participating in the first ADP, up to \$160 for taking medication during Med 1 (6-8 days, up to 13 days if necessary), \$200 for participating in the second ADP, \$40 for complying with the 6-8 day washout procedures, up to \$160 for taking medication during Med 2 (6-8 days, up to 13 days if necessary), \$250 for participating in the third alcohol-drinking paradigm, and a bonus of \$200 for completing all 3 drinking paradigms given the within-subjects design. Subjects will earn an additional \$10 per day for transportation during phases 2, 3 and 5. Subjects will also receive an additional \$10 for keeping each scheduled appointment, once they are enrolled (after the physical exam) for a total of \$190. Subjects will also have the opportunity to earn an extra \$36 during each of the self- administration periods as well as \$75 for computer tasks done at the outpatient and inpatients appointments. Lastly, they will earn \$30 for completing each of the two follow-up appointments. This progressively increasing payment structure was developed in order to motivate subjects to complete all phases of the study, since obtaining complete data in this within-subjects crossover study is the key to achieving the goals of the project. We are trying to avoid early drop out by using increasing incentives for completion of the entire study. Subjects will be reimbursed \$20 for valet parking at Yale New Haven Hospital for overnight stays during the ADP's. They will also be compensated \$25 if they are asked to come back for any repeat lab work (blood or EKG). If a participant comes in to be consented and decides, after learning more about the study, he/she is not interested in participating, we will discontinue the intake appointment and compensate you \$10 for his/her time.

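### The Aim 1-3 models should always carry a fixed period effect; a test for order effects with about 10 completers per group cannot justify leaving it out

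*Combined protocol and SAP*

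**What the plan says.** Section V.3 (Research Plan) describes a within-subject crossover: a pre-drug baseline alcohol-drinking session (ADP), Med 1 ending in a second ADP, a washout, then Med 2 ending in a third ADP. Its reason for the first session is this: "The baseline ADP will be used to familiarize subjects with the laboratory procedures and reduce order effects in the subsequent ADP sessions".

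Section V.4 (Statistical Considerations) says "we will test for order effects, although any such effects should be greatly minimized with the inclusion of the baseline session". It does not define the order effect or say what follows from the test. For Aim 1 the linear mixed model has treatment as a within-subject factor and baseline drinking as a possible covariate, followed by a rule that non-significant covariates are removed. The Aim 2 and 3 models have treatment, time within the session and random subject effects. None of them names period or sequence. The Power Analysis paragraph plans 30 completers, 10 per group, and does not define a group.

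On the washout, Section V.3 has "At least 6-8 day washout phase (length of washout based on hospital scheduling", and Section X.2 pays participants "for complying with the 6-8 day washout procedures". Section VI.2 says of memantine that "the mean terminal elimination half-life is 60-100 hours and it is eliminated renally" and that it "has been shown to have a linear pharmacokinetic profile". Nothing in the protocol connects the half-life to the washout.

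On safety, Section V.3 states that "medication doses will be tapered up and adverse events recorded on a daily basis". The Exploratory Aims paragraph evaluates adverse events under combination treatment, with no breakdown by period or by Med 1 treatment.

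**The concern.** In a two-period crossover, anything that changes between Med 1 and Med 2 (practice, boredom, season, change in habitual drinking) is a period effect. The baseline session may remove some first-visit novelty, but it does not replace a term in the model. The plan tests for order and is silent on what happens next, so the term could be left out after a non-significant result. With so few participants that result is likely even when a moderate trend exists.

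The NTX+MEM or NTX+NAC versus NTX contrast is at stake on drinking, craving and stimulation. Omitting period can bias it when the two orders are unequally represented among completers. When they are balanced, omission puts the period variation into the error term. Since the pilot is meant to supply effect-size estimates for later trials, both its point estimates and its SDs matter.

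The washout raises a different question: residual memantine in participants who received it in Med 1. The baseline session precedes all medication and cannot address that.

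**Working it through.** The plan gives no power figure or washout calculation to reproduce.

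**1. Power of a test for period.** Inputs: two-sided 5% (Section V.4); n = 10 per group, or 30 if all completers are pooled (Power Analysis). Assumptions: a balanced two-period, two-sequence comparison; trend expressed in SDs of the within-person difference. Noncentral t with noncentrality = trend × √n and n − 2 df:

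| Trend (SD) | n = 10 | n = 30 |
|---|---|---|
| 0.3 | 13% | 36% |
| 0.5 | 29% | 75% |
| 0.8 | 60% | 99% |

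**2. Bias if period is omitted.** Bias = trend × |n1 − n2| / n, where n1 and n2 are the completers in each order. A 5/5 split gives 0, 6/4 gives 2/10 = 0.2 of the trend, and 7/3 gives 4/10 = 0.4. The uneven splits are illustrations; the documents report none.

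**3. Error inflation under balanced orders, n = 10.** Set the period-adjusted SD to 1. A trend of 0.5 SD observed in the sample adds 10 × 0.25 = 2.5 to the residual sum of squares of 8, now on 9 df: √(10.5/9) = 1.080, or 8%. If 0.5 SD is instead the true trend, the expected variance is (9 + 2.5)/9 = 1.278, whose square root is 1.13, or 13%. I use 8% below as the lower of the two.

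**4. Cost of keeping period.** With balanced orders the critical t goes from 2.262 (9 df) to 2.306 (8 df), a ratio of 1.019. With 30 completers (29 to 28 df) the ratio is 1.002.

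**5. Washout in half-lives.** 6 days is 144 h and 8 days is 192 h. Shortest washout with longest half-life: 144/100 = 1.44. Longest with shortest: 192/60 = 3.2.

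**6. Residual memantine at the third ADP.** Assume first-order decay, with the last Med 1 dose on the second ADP day (Table 1: "Administer last doses of medications"). Residual = 2^(−hours/half-life). If Med 2 Day 1 falls 6-8 days after that dose and Med 2 lasts 6-8 days, the two ADPs are 11-15 days apart:
- 11 days, 100 h: 2^(−2.64) = 0.160
- 15 days, 60 h: 2^(−6) = 0.016

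Counting one day later (12-16 days) gives 0.136 and 0.012. If effect is proportional to level and orders are balanced, the NTX+MEM versus NTX contrast shrinks by half the residual: 0.8-8%, or 0.6-6.8% on the later count.

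**7. Residual on Med 2 Days 1-2.** At 7-10 days after the last dose, 6-31% of the end-of-Med-1 level remains. That level is itself below steady state. Superposing the doses in the Section V.3 taper table for a 6-8 day Med 1, and dividing by the 20 mg/day steady state 20/(1 − 2^(−24/half-life)), gives about 3-17%.

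**The case against.** The strongest reply is that the period-term harm is conditional. Section V.4 promises a test for order in these models, so an order term must be fitted at some point. The rule on non-significant covariates comes directly after baseline drinking, and a reader might infer that it will also be used to drop period; the text does not say so. Statisticians generate the randomization schedule, and nothing in the documents shows unequal orders. All this stands. It makes the omission an open possibility and not a stated plan, and the bias hypothetical. It does not answer the low power of the test or the loss of precision under balanced orders.

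A second reply is that the two-sequence structure behind the power figures is assumed, because group is undefined and Med 2 is described only as a different combination. That also stands. Pooling all 30 gives better power, though still only 36% at 0.3 SD.

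On the washout, three stronger readings are tempting:
- **That scheduling fixed the 6-8 day minimum.** The text gives a floor and then says length depends on scheduling, which may refer only to time beyond the floor. The absence of a stated rationale is all that can be claimed.
- **That carryover seriously distorts the drinking comparison.** At the minimum washout it amounts to about 1-8%, less with a longer washout or a Med 2 running to 13 days, and only for memantine given first.
- **That early Med 2 adverse events will be materially misattributed.** The memantine dose justification in Section V.3 reports adverse-event totals at 20 and 40 mg no different from placebo, and levels on Days 1-2 are well below steady state. A table with small cells could not settle the matter either way.

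**Conclusion.** The point holds as an inexpensive improvement to the analysis. The models should keep period whatever an order test shows, because at n = 10 that test would miss a 0.5 SD trend about 71% of the time (100 − 29). The figures assume a balanced two-period comparison and trends chosen for illustration. The documents give no SD, no expected trend and no split of orders.

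The washout is a separate and lesser matter. Its minimum is short relative to the protocol's own half-life and is unexplained. A reader might infer that a period term would deal with residual memantine. It would not, because carryover confined to memantine-first participants is not a common period effect. The estimated attenuation rests on effect being proportional to level, and it does not support calling the drinking contrast seriously compromised.

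**What to change.** 1. **Section V.4, opening paragraph and Aims 1-3:** state that period (Med 1 versus Med 2) is a fixed effect in every model and is retained whatever the result of any test for order effects, and that the rule on dropping covariates does not apply to it. This is a wording change costing one degree of freedom: about 2% in critical t with 10 completers and 0.2% with 30.

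2. **Sections V.3, VI.2 and X.2 (lesser):** the sponsor should reconcile the washout passages with the stated memantine half-life and give the rationale. No length is proposed here.

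3. **Section V.4, Exploratory Aims (optional):** list Med 2 adverse events by Med 1 treatment, with Days 1-2 shown separately. This uses data already collected and is descriptive only; it cannot establish whether misattribution is small.
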